11.0 Data and Safety Monitoring

11.1 Assessments and documentation of adverse events:

Adverse events and grade will be recorded at each follow-up visit. Serious adverse events will be collected and reported from the time patient signs informed consent until the first surveillance safety follow-up visit. Non-serious adverse events will be collected from the time of first study drug dosing until the first surveillance safety follow-up visit.

11.2 Reporting of serious adverse events:

The definition of serious adverse events (SAEs) is given in Section 9.2.

Each serious adverse event must be followed up until resolution or stabilization, by submission of updated reports to the designated person. An isolated laboratory abnormality that is assigned grade 4, according to CTC definition, is not reportable as an SAE; unless the investigator assesses that the event meets standard ICH criteria for an SAE. CTC grade 4 baseline laboratory abnormalities that are part of the disease profile should not be reported as an SAE, specifically when they are allowed or not excluded by the protocol inclusion/exclusion criteria.

When required, and according to local law and regulations, serious adverse events must be reported to the Ethics Committee and Regulatory Authorities.

Study Investigators will conduct continuous review of data and patient safety. The Investigator will submit twice yearly progress reports of these data to the Data Safety Monitoring Committee for review. The review will include: the number of patients enrolled, withdrawals, significant toxicities as described in the protocol, serious adverse events both expected and unexpected, dose adjustments, and responses observed. The PI maintains a database of all adverse events with toxicity grade and information regarding treatment required, complications, or sequelae. The Investigator will submit a copy of the AE spreadsheet along with a Progress Report to the Data Safety Monitoring Committee (DSMC) for review. Actual review dates will be assigned when the 1st patient is accrued.

The DSMC at the Wilmot Cancer Institute, University of Rochester provides oversight of study progress and safety by review of accrual and adverse events at twice yearly meetings or more often if concerns arise. Any adverse event requiring expedited review per protocol, including those occurring at participating sites, will be submitted to the Safety Coordinator of the DSMC at the University of Rochester for

determination as to whether further action is required. When patient safety is of concern, an interim meeting may be called

- Any serious adverse event that is serious, related AND unexpected must be reported within 10 calendar days to both the DSMC Safety Coordinator and the RSRB (see RSRB guidelines). The DSMC Chair will determine whether further action is required, and when patient safety is of concern, an interim meeting may be called.
- Serious adverse events that are related AND expected or unrelated AND unexpected will be reported to the DSMC for review at the quarterly meeting. SAE reports are expected to include sufficient detail so that the DSMC can determine the severity, toxicity grade, expectedness, treatment required, and a follow up report documenting resolution or if there are sequelae. Serious adverse events that require detailed reports (but not necessarily expedited) are expected, related, non-hematologic toxicities of grades 3, 4 or 5.

The Safety Coordinator administratively coordinates reports and data collection and prepares documents for the DSMC Chair and committee review. The Safety Coordinator will administratively monitor adverse event rates utilizing the report from the study database. If any study has had two or more of the same SAE's reported in a month or more than six of the same SAE's in six months, the DSMC will review the summary of SAEs, discuss events with Study Chair, and conduct a more detailed review with the Study Chair. The Data Safety Monitoring Chair will determine if further action is required.

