8.0 Study Treatment Toxicities

8.1 Oxaliplatin

Common Toxicities:

- Peripheral neuropathy (may be dose limiting)
- Nausea
- Vomiting
- Diarrhea
- Fatigue
- Abdominal pain
- Constipation
- Increased liver transaminases AST and ALT
- Anemia
- Thrombocytopenia

Less Common Toxicities:

- Leukopenia
- Anorexia
- Cough

- Back or myalgias (muscle aches)
- Arthralgias (joint aches)
- Edema
- Flushing
- Skin Rash
- Alopecia
- Dyspepsia
- Dysgeusia
- Hypersensitivity
- Local site reaction with redness or swelling
- Increase serum creatinine

Rare but serious:

- Anaphylaxis
- Chest pain
- Shortness of breath
- Palmar-plantar erythrodysesthesia (hand-foot syndrome, with redness and/or pain)
- Sepsis
- Death

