8.4 Short Course Radiation

Common Toxicities:

- Fatigue
- Diarrhea
- Rectal pain/pressure
- Perineal Skin irritation
- Dysuria

Less Common Toxicities

- Change in bowel habit
- Vomiting
- Abdominal Pain

Rare but Serious:

- Bowel Obstruction
- Fecal Incontinence
- Secondary Malignancy

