9.4 Severity of Adverse Events

Numerical grading of adverse events will follow the Common Terminology for Criteria for Adverse Events version 5.0 from the U.S. Department of Health and Human Services:

Grade 1: Mild; asymptomatic or mild symptoms; clinical or diagnostic implications only; intervention not indicated.

Grade 2: Moderate; minimal, local or noninvasive intervention indicated; limiting age-appropriate instrumental activities of daily living.

Grade 3: Severe or medically significant but not immediately life-threatening; hospitalization or prolongation of hospitalization indicated; disabling; limiting self-care activities of daily living.

Grade 4: Life-threatening consequences with urgent intervention indicated.

Grade 5: Death from AE.

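### Section 11.2 sets no reporting deadline for a drug-related death that is rated expected, and the protocol never says what counts as expected

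*Combined protocol and SAP*

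**What the plan says.** Section 11.2 sorts SAEs by relatedness and expectedness.

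- **Expedited route:** "Any serious adverse event that is serious, related AND unexpected must be reported within 10 calendar days to both the DSMC Safety Coordinator" and to the RSRB, with a pointer to RSRB guidelines.
- **Routine route:** "Serious adverse events that are related AND expected or unrelated AND unexpected will be reported to the DSMC for review at the quarterly meeting".
- **Content of reports:** "SAE reports are expected to include sufficient detail so that the DSMC can determine the severity, toxicity grade, expectedness, treatment required", together with follow-up to resolution or sequelae. Directly after that comes: "Serious adverse events that require detailed reports (but not necessarily expedited) are expected, related, non-hematologic toxicities of grades 3, 4 or 5".

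Section 9.4 defines the top grade: "Grade 5: Death from AE". Section 8.1 lists death for oxaliplatin under "Rare but serious", and Sections 8.2 and 8.3 do the same for leucovorin and 5-fluorouracil. Section 8.4 does not list death for short course radiation; its list of rare, serious toxicities ends with "Secondary Malignancy".

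Section 11.2 also says that the DSMC meets twice a year, or more often if there are concerns. That does not match the quarterly meeting named in the routine route. Nowhere do the documents define expectedness or name a reference against which to judge it.

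**The concern.** A death caused by study treatment is the worst safety outcome the protocol names. Whether it reaches the DSMC and the RSRB within 10 days depends on a single rating, expected or unexpected, for which the site has no stated standard. The only toxicity lists at hand name death for all three drugs, so a rating of expected is easy to defend. The detailed-report sentence then confirms that no expedited report is needed.

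The authors say in Sections 1.2 and 10.3 that they know of no similar study, safety is a secondary objective, and no toxicity stopping rule for the study is stated. DSMC review is therefore the main safeguard. Without a deadline, new patients could start the same regimen before the committee has reviewed a toxic death.

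**Working it through.** The plan gives no figure to reproduce. The check passes a grade 5 event through each rule in Section 11.2 and then sizes the possible wait.

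**Rule trace**

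1. Drug-related death, rated unexpected: meets every condition of "related AND unexpected must be reported within 10 calendar days", so the deadline is 10 calendar days.
2. Drug-related death, rated expected, non-hematologic: fails the unexpected condition, so it takes the routine route. The detailed-report sentence covers it but does not require speed.
3. Drug-related death, rated expected, hematologic: takes the routine route and falls outside the detailed-report sentence. The general expectation on the content of SAE reports still applies.
4. Death related to radiation only: not listed in 8.4. If Section 8 is the reference, it is unexpected and the 10-day deadline applies.

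Case 1 differs from cases 2 and 3 in its expectedness rating, and that rating has no reference. Case 2 needs no inference from Section 8 to exist: the detailed-report sentence itself names expected, related events of grade 5.

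**Longest wait for DSMC review in cases 2 and 3**

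- Quarterly meetings: 12 / 4 = 3 months.
- Twice-yearly meetings: 12 / 2 = 6 months.
- If events fall evenly between meetings, the average wait is half of that: 1.5 or 3 months.

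**Patients starting treatment during the longest wait, at even accrual**

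- Section 10.3 plans 40 patients over about 5 years: 40 / 5 = 8 per year. Over 3 months, 8 × 3/12 = 2; over 6 months, 8 × 6/12 = 4.
- The schema (Figure 1) gives N = 30. Over the same 5 years, which is an assumption, 30 / 5 = 6 per year: 6 × 3/12 = 1.5 and 6 × 6/12 = 3.

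**Does another rule catch a single death?**

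- The count trigger in 11.2 needs at least two of the same SAE in a month, or more than six in six months. One death is a count of 1 and meets neither. In this study one death is already 1/40 = 2.5% of patients (1/30 = 3.3%).
- Interim meetings are allowed when safety is of concern, but no clause says how soon the DSMC must be told of an expected death.
- Reporting to the ethics committee and regulators applies where local law requires it. The clause gives no time limit and does not single out deaths.

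**The case against.** The best defence is that routing by relatedness and expectedness is a deliberate scheme and that Section 11.2 leaves several ways for a death to surface early. Investigators review safety continuously, and SAE follow-up goes to a designated person. The Safety Coordinator monitors event rates from the study database, and the monthly count trigger makes sense only if reports arrive between meetings. The DSMC may meet at any time. RSRB guidelines and local law, which are not in the documents, may require prompt reporting of deaths. All of this stands as mitigation. What it does not supply is a deadline.

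Four stronger readings are tempting, and the documents do not support them.

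- **That the DSMC cannot learn of such a death before its next routine meeting.** The text fixes when the event is reviewed. It does not tell sites to hold the report until then.
- **That Section 8 makes death an expected event.** Section 8 is a list of treatment toxicities, and 11.2 does not refer to it. Section 9.2 treats death as an outcome of an event, so an assessor could rate the underlying fatal event unexpected. The classification is possible, not prescribed.
- **That a hematologic death escapes detailed reporting altogether.** It falls outside one sentence only; the general content expectation has no hematologic exception. The protocol also does not define which fatal events count as hematologic.
- **That the cited literature shows 5-year survival of about 91% as a general benchmark for these patients.** That figure comes from one watch-and-wait series. Other figures in Section 1.2 are at other times or lower, for example 80.8% at three years. The point does not rest on prognosis.

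**Conclusion.** The concern holds as a gap in the reporting rule. A drug-related death that is rated expected has no fixed reporting deadline in the protocol, and nothing in the protocol governs that rating. DSMC review could wait up to about 3 to 6 months, against 10 calendar days on the expedited route. About 2 to 4 further patients would start in that time at 8 per year, or 1.5 to 3 if the total is 30 over the same period.

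The range assumes even accrual and no interim meeting. Its width reflects the conflict between quarterly and twice-yearly meetings. A reader might take six months as the plan's interval, but the sentence that governs expected SAEs says quarterly, so six months is only the upper end of an unresolved contradiction. The Section 8 part of the argument concerns drug-related deaths only. The change is a worthwhile, inexpensive improvement to a stated rule; it does not affect the primary analysis.

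**What to change.** In Section 11.2:

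1. Send every grade 5 event in the SAE collection period of Section 11.1 that is at least possibly related to study treatment by the existing 10-calendar-day route to the DSMC Safety Coordinator and the RSRB, whatever its expectedness.
2. State that the listing of death in Section 8 does not make a fatal event expected, and name the reference for judging expectedness.
3. Remove the non-hematologic limit for grade 5 events from the detailed-report sentence.
4. Reconcile the quarterly and twice-yearly meeting frequencies.

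The cost is a few sentences of text and at most a few additional expedited reports over the study, on a route that already exists. Treatment, endpoints and sample size do not change.

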12.0 Data Confidentiality and Storage

During participation in the study, subject data including laboratory results, imaging, exams, treatments, and outcomes will be part of the patient's chart. Data extracted from the chart for the purpose of the study will be stored in the RedCap database.

Subjects will each have their own unique code in place of name, date of birth or other identifier that may be used in charting. The key will not be derived from patient data and will be available to the principle and/or sub-investigators. To avoid unauthorized disclosure of subject data with consent, the following safeguards will be in place:

- Not storing identifying information in the research database except unique subject code that will be used for subject identification
- Subject codes will be randomly assigned, and codes will be protected and treated as confidential as they link subject to data
- Security measures for physical and electronic data i.e.) locking up research files/logging out of electronic systems while they are unsupervised
- Using screensavers

- Shredding excess copies of paper documents

13.0 Data and Specimen Banking for Future Research Use

Upon consenting for study enrollment, participants will be given the option also to consent for banking of their rectal tissue specimen(s) for future use related to the study. The purpose of banking is to have the option to evaluate for genetic, histologic, or molecular information retrospectively following the initial study. This may be used to continue further research or clinical questions that may arise from our proposed study.

Consideration for access to these specimens will be determined by the principal investigator. Raw data from the study will be stored in the RedCap database, and participant specimens will be stored with pathology for 5 years. Both data and specimen(s) will be identified by a unique assigned subject code not derived from patient data as to protect confidentiality, with the key remaining with the principle investigator and/or sub-investigators.

Subjects will not be re-consented for use of their specimens if used in part of this study by the current principle and sub-investigators. The subject may request for their data or specimen(s) to be removed from the study or storage at any at the initiation of study or thereafter.

Optional Correlative Biomarker:

Patients will have the option to consent for additional correlative biomarker blood samples for future research use. Two 10.0 mL EDTA lavender tubes (total of 20.0 mL) will be collected at each time point – baseline, Cycle 6 Day 1 and time of post radiation assessment (if applicable). Both plasma and buffy coat samples will be collected. Within 1 hour of collection, centrifuge collection tubes for 10 minutes at 1600 x g. Transfer the supernatant into a conical tube. Remove the buffy coat (~1.0 mL) from the collection tubes and place in 1.5 mL cryotube. Centrifuge supernatant for an additional 10 minutes at 1600 x g. Divide the plasma into three cryotubes – two 3.0 mL tubes and one 1.5 mL tube. Freeze plasma and buffy coat samples in -80°C freezer. All samples should be labeled with subject ID number, study time point, collection date and sample type.

